## Definition and components of the PRS

The AD polygenic risk score used in this protocol will be derived from genome-wide SNP data using effect sizes from large, externally validated AD GWAS and meta-analyses, excluding the APOE locus so that APOE genotype can be modeled separately. Briefly, after standard quality control and ancestry checks, we will compute a PRS as the sum across selected SNPs of the number of risk alleles carried by the individual (0, 1, or 2) multiplied by the corresponding log-odds ratio for AD from the discovery GWAS. SNP selection and clumping will follow published best practices (e.g., linkage disequilibrium pruning and p-value thresholding) to balance predictive performance and parsimony.

The components of the PRS therefore include:

- Common autosomal SNPs associated with AD risk in prior GWAS, weighted by their reported effect sizes.
- Explicit separation of APOE  $\epsilon 2/\epsilon 3/\epsilon 4$  genotype, which will be modeled as an independent covariate (e.g.,  $\epsilon 4$  dose), consistent with evidence that optimal AD risk prediction treats APOE separately from the polygenic background.
- Optional incorporation of loci from integrative dementia scores (e.g., vascular, and neurodegenerative pathways) if they improve prediction in the pre-FIH Insilco phase; any such additions will be documented in the statistical analysis plan.

The raw PRS will be standardized (z-score) within an ancestry-matched reference population (e.g., external dataset plus early enrollees) and then categorized based on prespecified quantiles (e.g., lowest ~25%, next lowest 25%, next highest 25%, and highest ~25%), following prior work stratifying AD risk by PRS percentiles. These categories will be used for recruitment targeting (approximate balance of low, average, and high PRS) and for prespecified subgroup analyses of conversion risk.

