## **Polygenic risk scores (PRS) in Alzheimer's disease**

Late-onset Alzheimer's disease (AD) is highly polygenic, with common variants of small effect across the genome contributing to risk in addition to APOE  $\epsilon$ 4. Polygenic risk scores (PRS) aggregate the weighted effects of large numbers of AD-associated single nucleotide polymorphisms (SNPs), typically using effect sizes from genome-wide association studies (GWAS), to generate an individual-level measure of inherited susceptibility. In AD, such scores, especially when combined with APOE, can identify individuals at markedly elevated odds of developing disease and earlier age at onset compared to those in the lowest PRS strata.

Several large GWAS and meta-analyses have now demonstrated that AD PRS discriminate cases from controls with AUC values commonly in the 0.70–0.80 range, and that individuals in the highest PRS percentiles can have more than a ten-fold higher odds of AD compared to those in the lowest percentiles when stratified by APOE genotype. PRS performance has been replicated across independent European and non-European cohorts and shows a stepwise relationship with incident AD dementia, age at symptom onset, and amyloid deposition. These data support the feasibility of using PRS, in conjunction with APOE and biomarker measures, for risk stratification and enrichment of preclinical and prodromal AD cohorts.

In addition to traditional GWAS-based scores, recent work has explored integrative or “multi-domain” polygenic scores that combine loci implicated in neurodegenerative and vascular pathways, as well as deep-learning–based approaches to optimize SNP weighting and capture non-linear effects. Such integrative scores can improve prediction of dementia onset and may better reflect the heterogeneous biology of AD, including vascular and metabolic components. Together, this literature motivates the use of a validated, APOE-aware PRS as one input into a broader proteogenomic risk (PR) model to stage cognitively normal (CN) individuals along a preclinical AD continuum in this study.

This protocol describes a FIH 2-year observational study to evaluate the Incident Prediction & Risk model's ability to predict conversion among ApoE4-positive adults,

with intensive plasma proteomic, genomic risk assessment, , neurocognitive assessments, and wearable device data. I,

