#### Baseline staging:

- Calculate P&R model-derived risk for the following prodromal AD stages(CN, SCD, MCI Stage I, etc.).
- Assign participants to CN and MCI risk strata (low, average, high PRS or four quantile-based categories)

Cerebrospinal fluid (CSF):

This protocol does not require any research-mandated lumbar punctures or CSF collection. If a participant undergoes lumbar puncture purely for clinical reasons outside the study (e.g., to resolve diagnostic uncertainty as part of routine care), and if the clinical team and participant agree, residual CSF may be shared with the study for exploratory biomarker assays under a separate biobanking consent. No lumbar puncture will be performed solely for research purposes, and participation in the study is not contingent on undergoing a lumbar puncture.

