### 5.2 Secondary outcomes

- Time to conversion from CN to MCI Stage I (regardless of pTau217 status) and from CN to pTau217-positive status (biomarker conversion).

- Estimated ten-year conversion rates from CN to MCI Stage I, extrapolating from observed two-year data using survival/hazard modeling informed by external cohorts.
  - Hazard ratios for LOAD associated with P&R model-derived risk scores, PRS categories, and biomarker trajectories.
  - Cost per participant and per conversion event detected for different sampling strategies (fingerstick vs venous; frequency of in-person visits vs reliance on digital monitoring).
  - Incremental predictive value (AUC-ROC, net reclassification improvement) of continuous digital monitoring features (smell, location, activity, speech, EEG, sleep) beyond traditional risk factors and biomarkers.
- 

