## 6. Statistical Considerations

### 6.1 General approach

Data analyses will be primarily exploratory and hypothesis-generating given the FIH nature and modest sample size, but key performance metrics (e.g., AUC-ROC) will be estimated with confidence intervals. Observational protocol templates recommend prespecifying primary analyses and sensitivity analyses for observational cohorts.

Analyses:

- Compute AUC-ROC for the P&R model and alternative models for predicting conversion to pTau217-positive MCI Stage I within 24 months.
- Compare AUC-ROC across models (proteogenomic vs proteo-methylome-genomic) using DeLong's test or similar.
- Use Cox proportional hazards models to estimate hazard ratios for time to conversion as a function of baseline P&R risk, PRS, ApoE4 dose, and biomarker levels.
- Use logistic regression and time-dependent ROC analyses for binary conversion endpoints over fixed time horizons.
- Incorporate digital monitoring variables as covariates and evaluate incremental predictive performance.
- For cost-effectiveness, compare costs and detection yield of different biospecimen and monitoring strategies using simple decision-analytic models (incremental cost per correctly predicted conversion).

Missing data will be handled using appropriate methods (e.g., multiple imputations, mixed-effects models) depending on pattern and mechanism of missingness. Sensitivity analyses will evaluate robustness of results to missing data assumptions.

---

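### PRS quantile categories, not the standardised z-score, are named for the secondary hazard-ratio outcome and subgroup analyses, which costs power and risks non-finite estimates when events are few

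*Protocol*

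**What the plan says.** Under the heading on the definition and components of the PRS (section 2.1), the score starts out continuous: "The raw PRS will be standardized (z-score) within an ancestry-matched reference population". It is then "categorized based on prespecified quantiles (e.g., lowest ~25%, next lowest 25%, next highest 25%, and highest ~25" per cent), with the four quarters given as an example. The categories have two uses: they guide recruitment, to balance the PRS levels roughly, "and for prespecified subgroup analyses of conversion risk".

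Section 5.2 includes among the secondary outcomes "Hazard ratios for LOAD associated with P&R model-derived risk scores, PRS categories, and biomarker trajectories". Section 6.1 plans Cox models to estimate "hazard ratios for time to conversion as a function of baseline P&R risk, PRS, ApoE4 dose, and biomarker levels". It does not say whether PRS enters as a z-score or as groups.

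The number of groups is not settled. The PRS definition illustrates four, section 3.2 plans low, average and high thirds, and the baseline staging text in section 4.2 allows "low, average, high PRS or four quantile-based categories".

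The cohort is up to 90 people in section 2.1 and 100 in section 3.2, followed for 24 months. No conversion rate, expected event count, PRS effect size or test of PRS is stated. Section 6.1 describes the analyses as mainly exploratory.

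**The concern.** Cutting a continuous predictor into groups discards the ordering within each group. If the groups are then compared as unordered levels, a one-parameter question becomes a three-parameter one. In a cohort of 90 to 100, each quarter holds 22 to 25 people (90/4 = 22.5; 100/4 = 25), and few of them are likely to convert in two years.

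Two things are at stake. The category analysis may miss a PRS effect that the z-score would detect. And if PRS does predict conversion, the lowest quarter, which is the natural reference, is the group most likely to have no events. Every hazard ratio against it is then infinite or undefined. The protocol has the z-score anyway, and its only stated reason for the cut is that earlier work stratified by percentiles.

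**Working it through.** There is no power or event figure in the protocol to reproduce. Everything below rests on stated assumptions.

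**Inputs.** From the protocol: N = 90 (section 2.1), 24 months of follow-up, four groups of about 25% (PRS definition) or three (section 3.2). Assumed: PRS normally distributed, no dropout, two-sided 5% tests, conversion of 6%, 10% or 20% over 24 months (90 × 0.06 = 5.4, 90 × 0.10 = 9 and 90 × 0.20 = 18 events), hazard ratio 1.3 to 2.6 per SD.

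**Step 1, large-sample formula.** With D events, the Cox test on the z-score has noncentrality D × (ln HR)² on 1 df. Quartile indicators keep 86.1% of that information, spread over 3 df; a quartile trend keeps the same 86.1% on 1 df; thirds keep 79.3% on 2 df. For D = 9 and HR = 2.0:

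- z-score: 9 × 0.6931² = 4.32 on 1 df, power 55%
- quartiles: 0.861 × 4.32 = 3.72 on 3 df, power 34% (loss 21 points)
- thirds: 0.793 × 4.32 = 3.43 on 2 df, power 36% (loss 19 points)
- quartile trend: 3.72 on 1 df, power 49% (loss 6 points)

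Most of the quartile loss therefore comes from the extra degrees of freedom.

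**Step 2, simulation.** The formula is unreliable with sparse groups, so I simulated exponential event times (1,500 datasets per cell, Cox score tests, cuts at the normal quantiles):

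| Conversion (events) | HR per SD | Power: z-score | Power: quartiles, 3 df | Power: quartile trend | Lowest quartile empty | Lowest third empty |
|---|---|---|---|---|---|---|
| 6% (~5) | 1.3 | 10% | 5% | 8% | 41% | 27% |
| 6% (~5) | 1.5 | 15% | 7% | 13% | 46% | 32% |
| 6% (~5) | 2.1 | 37% | 17% | 29% | 65% | 51% |
| 6% (~5) | 2.6 | 57% | 29% | 45% | 74% | 61% |
| 10% (~9) | 1.3 | 12% | 8% | 11% | 18% | 10% |
| 10% (~9) | 1.5 | 21% | 11% | 18% | 26% | 15% |
| 10% (~9) | 2.1 | 55% | 34% | 46% | 44% | 30% |
| 10% (~9) | 2.6 | 76% | 48% | 68% | 58% | 42% |
| 20% (~18) | 1.3 | 20% | 11% | 16% | 3% | 1% |
| 20% (~18) | 1.5 | 41% | 23% | 34% | 7% | 2% |
| 20% (~18) | 2.1 | 86% | 63% | 80% | 19% | 8% |
| 20% (~18) | 2.6 | 97% | 82% | 92% | 31% | 15% |

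Monte Carlo error is a point or two per cell. A second set of runs for 10% conversion and HR 2.1 gave 57% against 34%, a loss of 23 points, with the lowest quartile empty in 46% of datasets. Cutting at the cohort's own quartiles takes the largest 3-df loss to 29 points.

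**Reading the table.** The 3-df loss runs from about 4 to 29 points. The trend loss is about 1 to 10, except at 5 events with HR 2.6, where it reaches 12 to 15. Empty reference groups are common at 5 to 9 events and much less so at 18. With N = 100, HR 2.0 and 10% conversion, power is 57% against 36%, so the larger target changes little.

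**The case against.** Several stronger readings are tempting, and the protocol does not support them.

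*That categories replace the continuous analysis.* Section 6.1 lists PRS as a Cox covariate beside ApoE4 dose and biomarker levels, and the text headed Practical use lists a PRS among possible Cox predictors and refers to per-unit hazard ratios. Both are compatible with a continuous PRS. But neither states the scale, and the only PRS hazard ratio named as an outcome in section 5.2 is by category.

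*That a large power loss is built into the protocol.* No 3-df test is specified. A trend test would lose far less. The event counts, effect sizes and choice of test are assumptions made here.

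*That the effect size follows from the background section.* The protocol reports that "AD PRS discriminate cases from controls with AUC values commonly in the 0.70–0.80 range". Converted by HR = exp(√2 × Φ⁻¹(AUC)), an AUC of 0.70 or 0.75 would give 2.1 or 2.6 per SD. But that AUC separates cases from controls, whereas the study's score excludes the APOE locus and is applied to 24-month conversion among ε4 carriers only. The weaker effects in the table are at least as plausible, and there the loss is as small as 4 points.

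*That the category hazard ratios are generally not estimable.* This depends on the event count, and thirds fare better than quarters.

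It is also fair to say that the analyses are labelled exploratory, that the cut follows earlier work, and that the small number of events limits any PRS analysis whatever its scale. These points lower the stakes. They do not give a reason to prefer groups over a score that is already available.

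**Conclusion.** The point stands in a limited form. For one secondary outcome and the PRS subgroup analyses, the protocol names a less efficient and more fragile form of the predictor than the one it has already computed, and it leaves the number of groups open between three and four. The size depends wholly on the assumed conversion rate, PRS effect and test: with 90 participants, about 4 to 29 points of power for an unordered quartile comparison, and about 1 to 10 for a trend. The more practical problem is a reference quartile with no events, in roughly 20 to 60% of datasets at about 9 events and 3 to 32% at about 18. The first primary aim rests on the AUC of the P&R model and the second on feasibility, so neither is affected.

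**What to change.** In the PRS definition and in section 5.2, make the hazard ratio per 1 SD of the PRS z-score, with its confidence interval, the inferential result for this secondary outcome, and state in section 6.1 that PRS enters the Cox model on that scale. Keep the PRS categories for recruitment targeting and for descriptive tables: number of participants, number of events and Kaplan-Meier curves by group. Settle on one number of groups for that purpose.

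The cost is a few lines of wording, with no new data, visits or participants. The small downside is that one log-linear coefficient is assumed; the descriptive table by category lets readers check whether that is reasonable.

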## **Personalized MCI and AD Hazard Ratio Determination**

In a Cox model with 5 covariates  $X_1, \dots, X_5$ , the hazard at time  $t$  is

$$h(t|X) = h_0(t) \exp(\beta_1 X_1 + \dots + \beta_5 X_5),$$

so the **combined** hazard ratio for a profile  $(X_1, \dots, X_5)$  versus a reference  $(X_1^*, \dots, X_5^*)$  is

$$\text{HR} = \exp [\beta_1 (X_1 - X_1^*) + \dots + \beta_5 (X_5 - X_5^*)].$$

ucdavis +2

Equivalently, if each factor's hazard ratio (per unit) is  $\text{HR}_k = \exp(\beta_k)$ , and the difference from the reference is  $\Delta X_k$ , then

$$\text{HR} = \prod_{k=1}^5 \text{HR}_k^{\Delta X_k}.$$

## Practical use

- Fit a multivariable Cox model with one or more of the following predictors-X.
  - Polygenic Risk score - stratified to 5 ApoE Genotyped Categories
  - EMR-Lifestyle Risk Score = Dementia Risk Score
  - Proteomic Risk Score - stratified to 5 ApoE Genotype Categories
  - mDNA Risk score
  - Proteome Structure Based Risk Score
  - circRNA based Risk Score
  - MRI based Risk Score
  - PET Scan based Risk Score
  - EEG based Risk Score
  - Neurocognitive based Risk Score
  - Metabolome based Risk Score
- Use the estimated coefficients (or per-unit HRs) to compute the linear predictor for each subject.
- Exponentiate that linear predictor to get a single combined hazard ratio relative to a chosen reference profile; this can then be scaled or categorized as a “risk score.” or some may call an Aging Score.

## 2.2 Insilco and in vitro lead-in (pre-FIH phase)

[name] and [name] are currently conducting Insilco analyses using existing, independently collected cohorts that include whole-genome sequencing (for APOE and PRS), plasma proteomics including pTau217, imaging, and longitudinal cognitive/clinical outcomes. The data referenced here already have IRB approval and participant consent, and no additional contact with participants will take place during this phase.

The goal of the Insilco work is to develop and calibrate a proteogenomic Progression and Risk (P & R) model that estimates the short-term hazard of conversion from cognitively normal (CN) or very mildly impaired to pTau217-positive MCI due to AD. The model integrates:

- A polygenic risk score (PRS) for AD (APOE-excluded) plus APOE genotype.
- Plasma proteomic features selected from prior multi-omic studies of dementia and brain health.
- DNA methylation features associated with proteomic and cognitive/brain phenotypes.
- Key plasma AD biomarkers (pTau217, A $\beta$ 42/40, GFAP, NfL).
- Standardized Baseline cognitive and functional measures.

Model development and comparison

We will develop and compare at least two classes of time-to-event models:

1. A proteogenomic P & R model, which combines PRS + APOE with a parsimonious panel of plasma proteins including pTau217 and grounded with cognitive-functional tests.
2. A proteo-methyl-genomic model grounded with cognitive-functional tests.
3. A proteo-methyl-genomic - emr-lifestyle risk - oura ring data risk model, - grounded with cognitive-functional tests.

For each model, we will:

- Split source cohorts into training and internal validation sets or use cross-validation.
- Fit Cox proportional hazards or related survival models with time to conversion to MCI/AD or pTau217-positive MCI as the outcome.
- Derive a continuous risk score (linear predictor) and estimate discrimination (Harrell's C, AUC/ROC at fixed horizons such as 2–5 years) and calibration (calibration plots, Brier scores).
- Compare models using C-index/AUC and pragmatic criteria (assay cost, number of markers, ease of clinical implementation) to select a single P & R model for the FIH study.

Derivation of CN and SCD 4 risk groups and their expected transition event rates

Using the selected P & R model, we will apply the fitted risk equation to CN participants in the external cohorts and estimate their predicted near-term hazard of conversion. We will then:

- Define 4 Categories CN individuals whose predicted 2–5-year conversion risk to MCI lies above a prespecified percentile cut-off (25 % lowest risk quartile, 25% next to lowest risk quartile, 25% next to highest risk quartile, and 25% highest risk quartile)
- Define 4 Categories of SCD whose predicted 2–5-year conversion risk to MCI lies above a prespecified percentile cut-off (25 % lowest risk quartile, 25% next to lowest risk quartile, 25% next to highest risk quartile, and 25% highest risk quartile)
- Estimate annual conversion rates within these model-defined groups (CN vs SCD), which are expected to differ by several-fold based on prior work showing strong stratification by proteomic, cognitive assessment, and multi-omic risk scores.

These estimated event rates (number of pTau217 positive MCI conversions per patient-years) are then used to justify the future FIH longitudinal sample size and follow-up duration described in Sections 1.2 and 3.2.

Fixed model for the FIH cohort

Once selected, the P & R model will be locked (fixed coefficients and included markers) before analysis of the FIH cohort. For each enrolled participant, we will calculate the P & R risk score at baseline and use it to:

- Assign CN participants to 4 CN Risk Levels and 4 SCD Risk Levels (per the thresholds derived above).
  - Generate individual predicted hazards of conversion for comparison with observed events (primary and secondary analyses).  
The FIH study itself is thus a prospective validation of a pre-specified P & R model developed entirely from existing data.
- 

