#### **3.3 Inclusion criteria**

- Age  $\geq 55$  years at enrollment.

- At least one ApoE4 allele documented by prior testing (e.g., prior genetic panel, research cohort genotyping, clinical ApoE testing).
- Whole-genome sequencing (WGS) data previously completed and participants willing to provide existing WGS data files (e.g., VCF, FASTQ, or equivalent) to the study team for polygenic risk score (PRS) calculation.
- If WGS is not available but targeted genotyping arrays covering AD risk loci are available, participants willing to provide these data for PRS calculation (the study will assess feasibility of array-based PRS on a case-by-case basis)
- 
- Cognitively normal or very mildly impaired at baseline, defined by:
  - The Ponto Test and digital cognitive assessment equivalent of a Global CDR 0 or 0.5, and no clinical diagnosis of dementia.
  - For CN and SCD, P&R model staging criteria will be applied (combining PRS, biomarker, and cognitive data).
- Subjects that do not currently qualify for MCI status. (ie with the equivalent of a g CDR 0.5 - 1.0 , and plasma or CSF pTau217 level above a validated cut-off for AD-MCI pathology.
- Ability to provide informed consent and to comply with study procedures.
- Willingness to wear/keep digital devices for continuous monitoring (e.g., smartphone app, wearable sensors, sleep device).
- Note on genetic testing: This protocol does not perform ApoE genotyping or whole-genome sequencing as a research procedure. Eligible participants must already have these tests completed through prior clinical care, prior research studies, or commercial/direct-to-consumer services, and must be willing to share the results and raw genomic data files with this study. Screening will confirm that (a) prior ApoE genotype shows at least one  $\epsilon 4$  allele, and (b) WGS or suitable array data exist and can be obtained for PRS calculation. Individuals without documented ApoE4 carrier status or without available genomic data for PRS are ineligible for this protocol.

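### Section 2.2 sets the risk levels on 2–5-year MCI risk in external participants with no stated ApoE4 or age restriction, but the study observes pTau217-positive MCI over 24 months in ApoE4 carriers aged 55 or over

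*Protocol*

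**What the plan says.** Section 2.2 of the protocol describes how the Progression and Risk model is built, how risk levels are cut, and how both are carried into the study.

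- **Goal.** The opening of section 2.2 gives the target as the short-term hazard of pTau217-positive MCI due to AD.
- **Model terms.** They include "A polygenic risk score (PRS) for AD (APOE-excluded) plus APOE genotype".
- **Fitted outcome.** Survival models are fitted with "time to conversion to MCI/AD or pTau217-positive MCI as the outcome".
- **Derivation population.** For the levels, "we will apply the fitted risk equation to CN participants in the external cohorts and estimate their predicted near-term hazard of conversion". SCD levels are defined in parallel. No restriction by ApoE4 status or age is stated.
- **Cut-offs.** Levels are defined by whether "predicted 2–5-year conversion risk to MCI lies above a prespecified percentile cut-off", and the bands are "25 % lowest risk quartile, 25% next to lowest risk quartile, 25% next to highest risk quartile, and 25% highest risk quartile".
- **Event rates.** The rates estimated in these groups count pTau217-positive MCI conversions per patient-year, and are to justify the study's size and follow-up.
- **Use in the study.** The model is locked. It is then used to "Assign CN participants to 4 CN Risk Levels and 4 SCD Risk Levels (per the thresholds derived above") and to produce individual predicted hazards, which are compared with observed events in the primary and secondary analyses.

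Section 3.3 admits only people aged 55 or over with "At least one ApoE4 allele documented by prior testing". Section 5.1 defines the primary outcome as conversion to pTau217-positive MCI Stage I over 24 months and requires plasma pTau217 above a validated cut-off.

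**The concern.** A locked model can be validated only against the quantity it predicts. Section 2.2 uses pTau217-positive MCI in two places, leaves the fitted outcome open in a third, and uses MCI without the biomarker condition in a fourth. The range of 2 to 5 years is also not a single horizon, so no absolute-risk threshold follows from it. If the lock settles on all MCI, or on a horizon longer than follow-up, the comparison of predicted with observed events would show an excess of predicted risk that says nothing about the quality of the model.

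The second matter is the derivation population. Because APOE is in the score, carriers sit higher on it than non-carriers if APOE raises risk. Quartiles taken in a mixed population need not divide an all-carrier cohort into quarters. With at most 90 participants (section 2.1) or 100 (section 3.2), divided again into CN and SCD, a thin lowest level would say little. The upper-strata analysis (exploratory aim 8) would have less contrast. The external per-level event rates, which feed the sample size, might not describe carriers.

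**Working it through.** The protocol gives no conversion rate, APOE hazard ratio, score spread, carrier share in the source cohorts, or share of MCI conversions that are pTau217-positive. Its only figure here is 25% per level, which holds by definition in the derivation set. Everything below is a sensitivity calculation on stated assumptions.

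**1. Endpoint.** Let *f* be the share of MCI conversions that are pTau217-positive. At the same horizon, a correct all-MCI prediction set against pTau217-positive events gives expected/observed = 1/*f*.

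- *f* = 0.9: 1/0.9 = 1.11
- *f* = 0.7: 1/0.7 = 1.43
- *f* = 0.5: 1/0.5 = 2.00
- *f* = 0.3: 1/0.3 = 3.33

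**2. Horizon, absolute risk.** With constant annual hazard *h*, risk by time *t* is 1 − exp(−*ht*).

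| *h* per year | 2-year risk | 5-year risk | Ratio |
|---|---|---|---|
| 1% | 2.0% | 4.9% | 2.46 |
| 3% | 5.8% | 13.9% | 2.39 |
| 5% | 9.5% | 22.1% | 2.32 |
| 10% | 18.1% | 39.3% | 2.17 |

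**3. Horizon, level membership.** Under proportional hazards, risk at *t* is 1 − S0(*t*)^exp(LP), where LP is the linear predictor. This rises with LP at every *t*, so ranks are the same at 2 and 5 years. In simulation, 100% of participants fell in the same quartile at both horizons.

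**4. Balance of levels.** Take score = ln(HR) × carrier + Normal(0, *s*), with carrier share *p* in the derivation set. Each cut-off *c* solves *p*·Φ((*c* − ln HR)/*s*) + (1 − *p*)·Φ(*c*/*s*) = 0.25, 0.50 or 0.75. The share of carriers below *c* is Φ((*c* − ln HR)/*s*). Assumed ranges: *p* 25–60%, HR 1.5–4, *s* 0.7–1.5.

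| Case | *p* | HR | *s* | Carriers in levels 1/2/3/4 (%) |
|---|---|---|---|---|
| Check: derivation set all carriers | 100% | any | any | 25/25/25/25 |
| Mildest | 60% | 1.5 | 1.5 | 21.5/24.2/25.9/28.4 |
| Middle | 25% | 2 | 1.0 | 11.0/19.0/27.2/42.8 |
| Most extreme | 25% | 4 | 0.7 | 0.8/4.7/21.0/73.5 |

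Of 90 participants, the middle case gives 9.9, 17.1, 24.5 and 38.5, against 22.5 in each level if the cohorts matched.

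**5. An offsetting selection.** Section 3.4 removes pTau217-positive MCI, and pTau217 is a model input. Assume *p* 30%, HR 2, 1.0 log-hazard per SD of pTau217, pTau217 higher by 0.5 SD in carriers, and SD 0.8 for the other terms. Carriers then fall 8.2/17.1/27.9/46.8%. If the 40% of carriers with the highest pTau217 are also removed, the split is 13.6/26.8/35.6/24.1%. The top level is no longer over-filled, but the lowest is still thin. This removal goes further than section 3.4, which excludes only people who have both MCI and a positive pTau217.

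**The case against.** The strongest reply is that nothing here is yet an error. Section 2.2 does not say that non-carriers are used; it is silent, and the derivation set may be fixed elsewhere. The text leaves open fitting pTau217-positive MCI and evaluating at 2 years, which would match section 5.1. The protocol never promises 25% per level among enrolled participants, and a carrier cohort sitting higher on a fixed external scale can be the correct result. Recruitment is balanced on PRS categories, and that PRS excludes APOE. Section 6.1 calls the analyses mainly exploratory.

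Much of this stands. A reader might infer that the levels will be badly unbalanced and the model miscalibrated. The documents do not support that. The imbalance runs from slight to severe with inputs they do not give, and the pTau217 exclusion can offset part of it. The horizon does not change level membership under proportional hazards. Cut-offs do not cause miscalibration, which would come from the fitted outcome and the baseline hazard. Because APOE is a model term, carrier status moves the score without making it wrong.

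A reader might also object to "Polygenic Risk score - stratified to 5 ApoE Genotyped Categories" on the ground that only three genotypes carry ε4. That list names candidate predictors for fitting a Cox model and does not say that five strata will exist in this cohort, so it is no defect.

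What the reply does not remove is the conflict within section 2.2: the levels are set on an endpoint that is not the study's own. This is more than missing detail.

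**Conclusion.** The point holds as an inconsistency to be resolved before the model is locked. Section 2.2 names different endpoints for the goal, fit, levels and event rates, gives a range in place of a horizon, and states no ApoE4 or age restriction on the population that supplies the cut-offs.

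The consequences are conditional. If all-MCI risk is used, predicted exceeds observed by 1.1 to 3.3 times, for pTau217-positive shares of 90% down to 30%. If 5-year risk is set against 24 months of follow-up, the excess is about 2.2 to 2.5 times, for hazards of 10% down to 1% per year. If the derivation set mixes carriers and non-carriers, the levels may lie anywhere between near balance and about three quarters of participants in the top level, and the per-level event rates behind the sample size need not represent carriers.

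The AUC on the continuous score in primary aim 1 does not depend on the cut-offs or on the horizon at which risk is expressed. The parts at risk are the four-level assignment, the predicted-versus-observed comparison, the upper-strata analysis and the event rates used for planning.

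**What to change.** Before the lock, amend section 2.2 to state one endpoint, one horizon and one derivation population:

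- fit the model to pTau217-positive MCI, removing the alternative of MCI/AD;
- report predicted risk at 24 months, and define the levels on that risk;
- derive the CN and SCD cut-offs and the per-level event rates in external participants with at least one ε4 allele and aged 55 or over.

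The endpoint and horizon gaps then close by definition. The expected share is 25% per level (22.5 of 90, or 25 of 100), apart from sampling error and any remaining differences in selection, such as the pTau217 exclusion.

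The cost is a re-run on external data already in hand. The derivation set will be smaller and the cut-offs less precise, so the number of external carriers and events behind each cut-off should be reported.
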